**NCT04977947**

**03/15/2020**

## Statistical Analyses and Power

### **1. Outcome assessment and definitions**

Our primary outcome for this study is infant Body Mass Index (BMI).

Outcome	Assessed when?	Metric(s)	Continuous or categorical	Maximal range	Hypothesized results
Infant anthropometry	Baseline, post-treatment	Percent of infants with BMI $\geq 85^{\text{th}}$ percentile, by treatment group	Categorical	0% to +100%	Intervention < Control
Infant anthropometry	Baseline, post-treatment	Pre- to post-study change in BMI percentile, by treatment group	Continuous	-99% to +99%	Intervention < Control

Our secondary outcomes are infant diet and intervention acceptability

Outcome	Assessed when?	Metric(s)	Continuous or categorical	Maximal range	Hypothesized results
Infant diet diversity	Baseline, post-treatment	Pre- to post-study change in number of food groups provided in previous day, by treatment group	Continuous	-7 to 7	Intervention > Control
Infant diet quality	Baseline, post-treatment	% kcal from fat  Servings vegetables+ fruits	Continuous	0 or greater	Intervention < Control  Intervention > Control
Treatment adherence	Throughout treatment	Proportion of treatment sessions completed by participants in the treatment condition	Continuous	0 to 6	At least 5 of 6 sessions completed
Treatment fidelity	25% of intervention visits	Provision of intervention components as specified in module	Continuous	Varies relative to module goals	<5% of module components not covered
Maternal feedback	Post-treatment	Proportion of mothers indicating positive view of program	Categorical	0% to 100%	>90% indicate positive view
Peer Counselor feedback	Post-treatment	Qualitative coding of themes	Qualitative	n/a	n/a

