| | 
involving stakeholders in a home- visiting program serving at-risk youth and their families.
 
Aim 2: Examine whether the HEMI program, a 6-month personalized obesity prevention program for infants, is effective and acceptable/relevant for families receiving home visiting services.
 
1.2 Describe the hypotheses to be tested.
 
We hypothesize that families and peer counselors involved in delivery of the program will find the treatment appropriate, satisfactory, relevant, and helpful as rated on a treatment satisfaction questionnaire, post-treatment debriefing interviews, and measurement of treatment completion rates. We also hypothesize families receiving the program (n = 15) will have a lower proportion of infants with BMI > 85th percentile compared to infants in control families who receive standard ECS content only (n = 15). Secondarily, differences in child diet between the treatment and control group will be examined.
 |

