| 
16.0 POTENTIAL BENEFITS TO SUBJECTS
 | 
16.1 Describe the potential benefits that individual subjects may experience from taking part in the research. It may be useful to include: the probability, magnitude, and duration of the potential benefits. Indicate if there is no direct benefit to subjects. Do not include benefits to society or to others.
 
Mothers may benefit from participation in the study through receipt of a potentially efficacious intervention to promote healthy infant feeding and reduce subsequent obesity-risk.
 |
| 
17.0 DATA MANAGEMENT AND CONFIDENTIALITY
 | 
17.1 Describe the data analysis plan, including any statistical procedures or power analyses.
 
Aim 1: GLA data analysis will be conducted in real-time by the participants during the session. Participants will reach consensus on overall themes and action items.
 
Aim 2: Proportion of infants with BMI ≥ 85th percentile will be compared between the treatment and control group using a Fisher's exact test of independence, including all randomized participants in an intention to treat framework. If baseline differences are found between groups, these baseline variables will be included in an adjusted logistic regression model with odds ratios of the intervention group estimated relative to the control group. Sensitivity analyses will examine the impact of treatment fidelity on intervention efficacy. Secondary outcomes of infant diet diversity and servings of fruits and vegetables will be evaluated using general linear models, adjusting for baseline characteristics as needed. Infant biological sex and participation in other supplemental nutrition programs (e.g., WIC) will be explored as potential moderators of treatment outcomes.
 
17.2 Describe the steps that will be taken to secure the data.
 |

TEMPLATE: RESEARCH PROTOCOL

| NUMBER | ACTIVE DATE | PAGE |
|---------|-------------|----------|
| HRP-503 | 02-04-2020 | 21 of 44 |

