### **2. Analyses**

For Aim 1, GLA data analysis will be conducted in real-time by the participants during the session. Facilitated by Co-I [name], participants will reach consensus on overall themes and action items, such as the content to be included in each treatment module. Demographic information of stakeholders will be summarized using descriptive statistics.

**For Aim 2**, descriptive statistics of the study population will be summarized. Treatment adherence will be assessed as the number of treatment visits completed within 1 week of the monthly time window. Missed visits will trigger an analysis of the situation and attempted communication with the mother to gather additional information about why study visits were not completed. Treatment fidelity will be assessed using coding of audiotapes for 25% of the visits. The maternal feedback on the program will be conducted at the post-treatment visit, and qualitative/open ended questions will be coded and analyzed for themes for improvement of the intervention. Peer counselor feedback on the program will be assessed through interviews after all treatment sessions have been delivered. Responses to open-ended questions will be analyzed for themes and also used to further modify the intervention.

For all Aim 2 effectiveness outcome variables, analyses will be conducted using two-sample t-tests or non-parametric Wilcoxon rank sum tests to evaluate between-group differences for continuous variables, and Fisher's exact tests of contingency tables for categorical variables. Prior to conducting analyses, distributions of outcome variables will be assessed to determine the appropriate modeling approaches. All primary analyses will be conducted using intention to treat (ITT) analysis, including all individuals who were enrolled. Given the small sample size, imbalances may arise between the randomized study groups. If groups are unbalanced at baseline, these baseline variables will be included in adjusted general linear model or logistic regression models, depending on the outcome, with adjusted differences in outcomes estimated by intervention group. P-values  $< 0.05$  will be considered significant. Every attempt will be made to collect demographic and psychosocial covariate measures. However in the event of missing covariate data, we will use multiple imputation techniques to handle missing data in the statistical models.

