### **3. Statistical Power, Aim 2**

Primary outcomes: Data from a previous study in the *ECS* population identified that 31% of infants had  $\text{BMI} \geq 85^{\text{th}}$  percentile at age 9 months. Assuming this represents the *ECS* control population for this pilot study, 15 infants per group would provide 42% power to detect the reduction of this rate to 0% by 9 months in the intervention group, at  $p < 0.05$ . A similar power (43%) was obtained when modeling continuous change in  $\text{BMI}$  percentile between 3 and 9 months of age, which had a mean (SD) change of 19.6 (29.3) percentile points, assuming the intervention group would achieve no mean change in  $\text{BMI}$  percentile and equal variance with the control group. Thus, this study will be underpowered to identify significant changes due to the intervention, but will enable estimation of the effect size to power larger studies.

Secondary outcomes: Previous observational data from a cohort of Cincinnati infants living in an urban environment found that the number of food groups fed increased by an average of  $3.4 \pm 1.4$  food groups between ages 3-9 months. (Woo 2015) Assuming equal variance between the intervention and control groups, and 15 infants per group, this pilot study would have 75% power to detect a 1 SD (1.4 food group) difference in the increase of food groups between intervention groups at  $p < 0.05$ . We thus anticipate that this pilot intervention will also be underpowered to evaluate changes in our secondary outcomes of infant diet, but will be informative with regard to the anticipated effect size and resulting sample size required in a larger trial.

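### The SAP lists two unranked primary BMI metrics, each tested at p<0.05, while the protocol analyses only one and names no primary endpoint

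*SAP*

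**What the plan says.** SAP section 1 opens with "Our primary outcome for this study is infant Body Mass Index (BMI"). The table below that sentence has two rows. The first is categorical and begins "Percent of infants with BMI", with the cut-off at or above the 85th percentile. The second is continuous: "Pre- to post-study change in BMI percentile, by treatment group". Each row has its own hypothesised result, and neither is marked as the deciding one. SAP section 3 puts both under a plural primary label and gives each its own power, 42% and 43%.

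SAP section 2 covers testing: "For all Aim 2 effectiveness outcome variables, analyses will be conducted using two-sample t-tests or non-parametric Wilcoxon rank sum tests" for continuous variables, and Fisher's exact test for categorical ones. P-values below 0.05 "will be considered significant". There is no order of testing, no rule on whether one or both metrics must succeed, and no multiplicity adjustment.

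The protocol has one BMI hypothesis (section 1.2): treated families "will have a lower proportion of infants with BMI > 85th percentile compared to infants in control families". It has one BMI analysis (section 17.1), in which the proportion "will be compared between the treatment and control group using a Fisher's exact test of independence". Change in BMI percentile does not appear in that analysis plan. Diet is called secondary there, but the proportion is never called primary. Section 5.1, the place for endpoints, gives only dates.

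**The concern.** With two unranked primary metrics and one significance threshold, the choice of which result is the primary one is left open until the data are in. Two things are at stake. One is the error rate, because two tests give two chances of a nominally significant primary result. The other is the reading of the trial. The two metrics use the same measurements differently, one through a threshold at 9 months and the other through change from baseline, so they can easily give different answers. The effect size carried into a larger trial would then also be open to selection, because the more favourable metric could be chosen after the fact.

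**Working it through.** **Inputs.** From SAP section 3: 15 infants per arm; a control rate of 31%, from a study in the ECS "population identified that 31% of infants had" a BMI at or above the 85th percentile at 9 months; a control change of 19.6 percentile points (SD 29.3), against no mean change in the intervention arm. From SAP section 2: Fisher's test and the t-test, each at 0.05. Assumed: two-sided tests, complete data, and normally distributed BMI z-scores with SD 1. The correlation between baseline and post-treatment z-scores is not given, so a range is shown.

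**1. The SAP's own power figures.**
- Continuous: standardised effect 19.6/29.3 = 0.669; noncentrality 0.669 × √(15/2) = 1.83; two-sided t-test on 28 df. Power is 42.4%, against 43% stated. This reproduces.
- Proportion, 31% vs 0%: with no events among the treated infants, Fisher's test needs at least 5 of 15 in the control arm. P(X ≥ 5), X binomial(15, 0.31), is 51.9%, against 42% stated. This does not reproduce. It is a separate matter and does not affect the point here.

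**2. Error rate if either metric may count.**
- Nominal, independent tests: 1 − 0.95² = 9.75%.
- Fisher's true size at 31% in both arms, by exact enumeration: 1.7%. Its maximum over all common rates is 1.8%.
- Upper bound with the planned tests: 5.0% + 1.8% = 6.8%. If independent, at 31%: 1 − 0.95 × 0.983 = 6.6%.
- Simulated on the same infants (200,000 trials per setting; mean z −0.17 at baseline and 0.54 at 9 months in both arms, which gives 31% at or above the 85th percentile and a mean change of 19.6 points): 6.4% to 6.6% for correlations from 0.2 to 0.8. Replacing the t-test by Wilcoxon gives the same range.
- Significance in the hypothesised direction only: 3.2% to 3.3%, against 2.5% for a single test.
- If both metrics had to be significant: 0.1% to 0.3%.

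**3. How often the two tests disagree under the SAP's continuous effect.** Control arm as above. In the intervention arm the mean z stays at −0.17, so the mean change is zero and the share at or above the 85th percentile is 1 − Φ(1.036 + 0.17) = 11.4%. Simulated, 200,000 trials per row:

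| Correlation | SD of change, control arm | t-test significant | Fisher significant | Both | Exactly one |
|---|---|---|---|---|---|
| 0.3 | 33.5 | 33.5% | 13.9% | 7.7% | 32% |
| 0.5 | 28.8 | 43.4% | 13.8% | 8.5% | 40% |
| 0.7 | 23.0 | 62.3% | 13.8% | 10.1% | 56% |

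The last column is the t-test column plus the Fisher column minus twice the both column; at 0.5, 43.4 + 13.8 − 17.0 = 40.2. The middle row comes closest to the SAP's SD of 29.3.

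**The case against.** The strongest defence is that this is a 30-infant pilot. SAP section 3 says openly that it lacks the power to show an effect and is meant to gauge the effect size for a larger study. In such a trial the familywise error rate is not the main operating characteristic, and an excess of about 1.5 points does little harm. That stands, and it lowers the weight of the point. It does not remove it. SAP section 2 still sets a significance threshold, SAP section 1 states directional hypotheses, and protocol section 6.1 gives efficacy as one of the things to be assessed. A larger study must also be sized on one of the two metrics.

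A reader might infer that the plan allows success on either metric, and so has an error rate above 5%. The documents do not say that. They contain no success rule at all, and a rule requiring both metrics would put the error far below 5%. The 6.5% is what an either-metric reading would cost.

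A reader might also infer that the two documents designate different primaries. They do not. The protocol implies the proportion by contrasting it with secondary diet outcomes, but it formally designates nothing. The fault is a missing designation in the protocol and an unranked extra metric in the SAP.

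**Conclusion.** The point holds as an ambiguity that should be closed. The SAP has two unranked primary BMI metrics at p<0.05 each, the protocol plans one BMI analysis without calling it primary, and nothing prevents a claim on either metric.

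The error-rate cost is small: about 6.5% if either counts. The nominal 10% is not reached, mainly because Fisher's test is so conservative at 15 per arm. The more practical cost is that exactly one of the two tests is significant in about 40% of trials at the correlation that best matches the SAP's SD, and in 32% to 56% over correlations of 0.3 to 0.7. These figures rest on two-sided tests, complete data, normal z-scores, the SAP's control rate and change, and an assumed correlation. The documentary gap does not depend on any of them.

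**What to change.** Before any outcome is compared by arm:

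- Name one primary metric, with its time point, in protocol sections 1.2, 5.1 and 17.1 and in SAP sections 1 and 3. The proportion at or above the 85th percentile at 9 months fits the protocol as it stands. If the sponsor prefers change in BMI percentile, amend the protocol to match.
- If the proportion is kept, use one cut-off throughout. Protocol section 1.2 says above the 85th percentile, while section 17.1 and the SAP say at or above it.
- Move the other metric to secondary or supportive, and limit the p<0.05 claim to the primary.
- Report both estimates with confidence intervals, which serves the stated effect-size aim whichever metric is chosen.

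The cost is a few lines of text, with no added infants or data. The sponsor gives up a second route to a positive primary result. Keeping the proportion also means relying on a test that uses about 1.7% of its 5%, and that is significant in only about 14% of trials in the scenario of step 3. Splitting alpha to keep both metrics as primary would bring the error to about 3.3%, but power would fall to 31.2% (t-test, from 42.4%) and 30.8% (Fisher, 31% vs 0%, from 51.9%). Designating one metric is the cheaper choice.

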Peer Counselor Feedback on the Intervention: Interviews will be completed with peer counselors after all study participants have completed treatment. Open-ended questions will be asked such as: What aspects of the intervention did you feel were most helpful for families? What are additional things not currently offered in the intervention that you think could be helpful to families? Did you feel adequately

TEMPLATE: RESEARCH PROTOCOL

| NUMBER | ACTIVE DATE | PAGE |
|---------|-------------|----------|
| HRP-503 | 02-04-2020 | 14 of 44 |

trained to provide the intervention? How do you feel participants utilized your role as a peer counselor? How could the peer counselor sessions be improved?

Infant Anthropometrics: Infant weight and length will be measured in duplicate at each in person treatment and study visit using a mobile digital SECA baby scale and portable infant length board. The scale will be calibrated using a known weight, and will be zeroed prior to assessment. Infants will be weighed in a clean diaper without clothes. The length board has a stable headboard and a moveable foot board, and will be placed on a flat, hard surface. All length measurements will be taken using the right leg, with assistance from the mother as needed to hold the infant still while the right leg is extended flat and the foot flexed against the foot board. Weight measurements will be taken to the nearest 1.0 gram and length measurements to the nearest 0.5 cm. Infant BMI standardized for age and sex will be calculated from the WHO 2005 growth standards.

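### The continuous BMI primary is change in percentile, a bounded non-linear scale, so the effect size the pilot hands to later trials depends on where infants start

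*SAP*

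**What the plan says.** SAP section 1 names infant BMI as the primary outcome and lists two metrics for it. One is the percentage of infants at or above the 85th BMI percentile. The other is "Pre- to post-study change in BMI percentile, by treatment group", a continuous score with a stated range of -99 to +99.

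SAP section 2 compares continuous outcomes by two-sample t-test or Wilcoxon rank sum test, after looking at the distributions to choose a modelling approach. Protocol 17.1 gives an analysis only for the proportion, which "will be compared between the treatment and control group using a Fisher's exact test of independence".

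SAP section 3 powers the continuous metric on the percentile scale, from prior data with a "mean (SD) change of 19.6 (29.3) percentile points" between 3 and 9 months. It reports 43% power, concedes that the study is underpowered, and gives effect-size estimation for larger trials as the purpose.

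Protocol 6.5 (Infant Anthropometrics) states: "Infant BMI standardized for age and sex will be calculated from the WHO 2005 growth standards". Neither document names a z-score outcome.

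**The concern.** A percentile difference is not a fixed amount of BMI. Near the median a small change in standardised BMI moves many points; in either tail a large change moves few. Averaging such differences gives an infant's change a weight that depends on its starting position.

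Two things are at stake. First, the proportion at or above the 85th percentile records whether an infant is over the cut, not how far. If the continuous metric is also insensitive there, neither primary metric measures change in that region well. The region matters to this trial: Protocol 2.3 presents BMI at or above the 85th percentile at 6 and 12 months as a strong predictor of later obesity, and the SAP's prior study "identified that 31% of infants had" BMI in that range at 9 months. Second, the pilot's main quantitative product is an effect size. A mean percentile difference carries the starting distribution of these 30 infants with it, so it transfers imperfectly to another population.

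**Working it through.** **1. The plan's own figure.** Inputs from SAP section 3: control change 19.6, SD 29.3, intervention change 0 ("assuming the intervention group would achieve no mean change in" BMI percentile), equal variance, 15 per group, 0.05 taken as two-sided.
- Standardised difference: 19.6 / 29.3 = 0.669.
- Noncentrality: 0.669 × √(15/2) = 1.832.
- Power by noncentral t with 28 df: 42.4%. Normal approximation: Φ(1.832 − 1.960) = 44.9%.

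The stated 43% reproduces, so there is no arithmetic error.

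**2. The compression.** With percentile = 100·Φ(z), the local exchange rate is 100·φ(z) points per z.

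| Start | z | Points per 0.1 z | Points for a 0.5 z rise |
|---|---|---|---|
| 50th | 0 | 4.0 | 19.1 |
| 85th | 1.04 | 2.3 | 8.8 |
| 95th | 1.64 | 1.0 | 3.4 |
| 99th | 2.33 | 0.3 | 0.8 |

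By symmetry the same holds in the lower tail. As an extreme illustration, 85th to 99.9th is 3.09 − 1.04 = 2.05 z and scores 14.9 points; 42.5th to 57.4th is 0.19 + 0.19 = 0.38 z and also scores 14.9.

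**3. Dependence of the group effect on the starting distribution.** If z ~ N(m, 1), the mean percentile is 100·Φ(m/√2). Take a uniform reduction of 0.5 z.
- From m = 0.54 (which puts 31% at or above the 85th): 64.9 − 51.1 = 13.8 points.
- From m = 1.54 (an assumed heavier population): 86.2 − 76.9 = 9.3 points.

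The effect is the same in z and differs by about a third in points.

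**4. Power, z against percentile.** The documents give no z-score mean, SD or correlation, so these are assumed. The model is bivariate normal z, with SD 0.8 to 1.2 at each age, calibrated to the SAP's 31% at 9 months, mean change 19.6 and SD 29.3. The implied correlation is 0.27 to 0.59. Each scenario used 20,000 simulated trials, 15 per arm, a two-sided t-test at 0.05, and both scores from the same data.

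| Effect | z | Percentile |
|---|---|---|
| Uniform shift cancelling the control rise (0.65 to 0.78 z) | 43–47% | 40–44% |
| −1 z only in infants ≥85th | 12–14% | 8–10% |
| Infants above the 85th brought down to it | 7–9% | 5–6% |
| Positive z halved | 15–19% | 10–14% |
| −1 z only in the middle range (absolute z < 0.67) | 15–20% | 19–24% |

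Under the uniform shift the gain from z runs from −0.5 (43.4% v 43.9%) to about +6 points (45.7% v 40.0%), typically +3 to +5.

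A simpler model (baseline N(−0.1, 1), 9-month N(0.54, 1), correlation 0.45; control change about 17.7 points, so only close to the SAP inputs) gives 30% on z against 40% on percentile for a −1 z effect confined to infants between the 50th and 95th at 9 months.

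**5. Does Wilcoxon repair it?** No. The difference is taken after the transform, so the ranks are of compressed differences. Under the uniform shift, Wilcoxon power was 40–44% on z and 38–41% on percentile change.

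**6. A later trial.** For 80% power, n per arm = 2(1.960 + 0.842)²/d². On percentile, d = 0.669 gives 36. On z, d = 0.68 to 0.71 gives 34 to 31.

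**The case against.** The strongest case for the plan has four parts.

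- **Power.** A reader might infer that percentile change always has less power than a z-score from the same infants. It does not: the sign depends on where the effect lies, and percentile wins by 4 to 10 points for mid-range effects. For an effect in infants below the 85th at baseline, arguably the prevention case, the simpler model gives 30.2% on z and 29.5% on percentile, which is effectively equal. This part stands.
- **Target population.** A reader might also infer that the programme targets infants who already have excess weight, so that the metric neglects its own target. The documents do not support that. Protocol 1.1 describes prevention in at-risk infants, and the entry criteria in Protocol 6.2 and 10.2 set no weight or BMI limit. Most infants would be below the 85th percentile, where the scale is least compressed near the median. This part stands too.
- **The other primary metric.** The proportion at or above the 85th is the protocol's stated hypothesis and looks directly at crossing into the high range. That is true, but it is silent on movement above the cut.
- **No data are lost.** Weight and length are recorded, so z can be computed later. This limits the harm. It does not replace prespecification, and it does not make the planned effect size portable.

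The check of distributions in SAP section 2 chooses a model; it does not change the metric.

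**Conclusion.** The point holds as one about choice of metric. The scale is bounded, both tails are compressed, equal changes in standardised BMI score differently by starting position, and neither primary metric measures change above the 85th percentile well. That weakens the effect size the pilot is meant to deliver.

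The practical size is modest: about 31 to 34 against 36 per arm in a later trial under a uniform shift, and a mean difference in points that shifts with the starting distribution. No general power deficit should be claimed; the gains and losses from z are those in the working. They rest on normal z-scores with assumed SDs and correlations, calibrated to prior data for 3 to 9 months, whereas the trial runs from 2 to 9 months. The SAP's 43% is correct on its own terms.

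**What to change.** In SAP section 1, make the continuous primary metric change in WHO BMI-for-age z-score from baseline to post-treatment, or 9-month z adjusted for baseline z. At minimum, prespecify one of these beside percentile change. Commit to reporting the z-score SD, the between-group difference and its confidence interval, since those are what a larger trial needs. Keep percentiles as description or as a supporting analysis. In SAP section 3, restate the power figure in z units if the prior ECS data allow; if they do not, say so and keep the percentile figure for the supporting analysis.

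The cost is SAP wording and one recalculated figure. Weight, length and the WHO standardisation are already planned. The downsides are a less familiar unit for lay readers and some loss of power if the effect lies only in mid-range infants.
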